#### 4.1.2. Baseline Definition

For all visit-based endpoints, including the co-primary endpoint of endoscopic NP score, baseline will be defined as the latest non-missing measurement collected prior to the first dose of study treatment. This will generally be from the Day 1 (Visit 2) assessment but may be from an unscheduled or screening assessment. In the case a visit-based assessment was collected after the first dose of study treatment, but still on the day of the randomization visit on Day 1 (Visit 2), then that assessment may be used.

For daily efficacy endpoints collected in the eDiary, baseline will be the average score from the 28 calendar days up to and including the date of randomization. This means the average will be based on the non-missing data from Day -27 to Day 1 inclusive. There must be a minimum of 4 non-missing values from Day -6 to Day 1 inclusive in order to derive the baseline, otherwise it will be set to missing.

Unless otherwise stated, if baseline data is missing no derivation will be performed and baseline will be set to missing.

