	Ŏ	2a	3ª	40	5a	6b	7a	86	ga .	1U ^a		120	13ª	140	15ª	10a	a, e	b, e	scan must be performed prior to randomization and should be the last assessment performed, where possible. If the first CT scan cannot be performed as the last assessment before randomization, the subject should have completed their screening visit and all screening lab results, the central NP score and ECG central over-read results should be assessed by the PI before a CT scan is conducted. The second CT scan should be performed at V16 or EW visit (up to 14 days prior to the nominal study visit). Note: If a participant is permanently discontinued both from the study intervention and from the study, and the second dose of study intervention was not received, decision on performing CT scan during EW visit at Week 26 will be made by the investigator in consultation with the Medical

	(Visit 1)a, d						Tr	eatn	nent	Peri	od						Withdraw	/Follow Up	
Procedure	Ξ							1	Weel	k							EW Visit	Follow-up	Notes -
1 Toocdard	Screening	0	4	8	12	16	20	24	26	28	32	36	40	44	48	52	26 or 52	30/56	Notes
	eel									Vi	sit (±	-7 da	iys)						
	Sci	2a	3a	4 c	5a	6 ^b	7a	8 b	9a	10a	11a	12 ^b	13a	14b	15ª	16a	a, e	b, e	
																			Monitor. Please refer to Pregnancy test (WOCBP only).
Assessment of Actual NP Surgery or planned NP Surgery		Х	Х	Х	Х	Х	X	X	X	Х	X	X	X	Х	X	Х	Х		Wherever possible (and when optional consent provided for exploratory biomarkers), the removed tissue from a nasal surgery will be collected and stored. Not applicable for China.
Assessment of systemic CS and antibiotics dose and duration including for CRSwNP		Χ	Χ	Х	Х	Χ	Χ	Χ	Χ	Χ	Χ	Χ	Χ	Χ	Χ	Χ	Х	Х	
Patient-Reported Outcomes																			
Dispensing and Training of the eDiary	Χ																		
eDiary Compliance Check		Χ	Χ	Χ	Χ	Χ	Χ	Χ	Χ	Χ	Χ	Χ	Χ	Χ	Χ	Χ	Х		
eDiary Collection																Χ	Х		
Individual symptom scores (including nasal obstruction, rhinorrhea [runny nose], loss of smell, facial pain, and mucus in throat) (VRS) ^f	Χ	Χ	X	Х	X	X	Χ	X	X	Χ	Χ	Χ	Χ	Χ	X	Χ	X		Performed using eDiary. eDiary will be completed by participants in the morning between Screening Visit (V1) and V16.
Overall symptoms score (VAS) ^f	X	Х	Χ	х	Х	Х	Χ	Χ	Χ	Х	Х	Χ	Χ	Х	Χ	Χ	X		Performed using eDiary. eDiary will be completed by participants in the morning between Screening Visit (V1) and V16.
Nasal obstruction score (VAS)f	Χ	Χ						Χ								Χ	Х		Performed using eDiary.
SNOT-22f		Χ	Χ	Χ	Χ	Χ	Χ	Χ	Χ	Χ	Χ	Χ	Χ	Χ	Χ	Χ	Х		Performed using eDiary.

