- e. If a participant withdraws from the study, then the EW Visit should be conducted 26 weeks after the last administered dose of study intervention, i.e., at Week 26 if the second dose of study intervention was not received, or at Week 52 if the second dose of study intervention was received. A follow-up visit/call should also be conducted 30 weeks after the last dose of study intervention for AE/SAE assessments, concomitant medication review and pregnancy testing (i.e., at Week 30 or 56).
- f. All questionnaires should be performed before any other assessments on each particular visit.
- g. Informed consent for optional genetics sample or optional exploratory biomarker samples (blood, surgery or nasal biopsy) must be obtained before collecting any samples.
- h. **China only**: Optional samples (genetics, exploratory biomarkers, surgery and nasal biopsy samples) will not be collected from participants in China. Urine dipstick will not be performed in China, all urine sample will instead be sent for central laboratory urinalysis. Investigators should be aware of the time needed for central laboratories to return results, and should perform appropriate local investigations if any urgent result is required.

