5.3. Randomization Criteria

Those participants who meet the randomization criteria below will be randomized into the study until the target of approximately 250 randomized participants is reached.

In rare instances and following consultation with the Medical Monitor a participant can be rescreened. Rescreened participants are required to sign a new ICF.

At the end of the run-in period, study participants must fulfill the following additional criteria in order to be randomized to study treatment:

- 1. Endoscopic bilateral NP score of at least 5 out of a maximum score of 8 (with a minimum score of 2 in each nasal cavity) taken at Visit 1 as assessed at central laboratory
- 2. Mean nasal obstruction VRS of 2 or greater over the last 7 days preceding Visit 2 (excluding Visit 2) (from electronic diary [eDiary])
- 3. eDiary compliance for at least 4 out of the last 7 days preceding Visit 2 (excluding Visit 2).
- 4. Not had any NP surgery between Visit 1 and Visit 2 and not on a waiting list for NP surgery at the time of randomization.
- 5. Laboratory abnormality: No evidence of clinically significant abnormality in the haematological, biochemical or urinalysis screen at Visit 1, as judged by the investigator.
- 6. Liver Chemistry Tests: obtained at Visit 1:
 - ALT $\leq 2x$ upper limit of normal (ULN)
 - Bilirubin ≤ 1.5x ULN (isolated bilirubin >1.5x ULN is acceptable if bilirubin is fractionated and direct bilirubin <35%)
- 7. ECG: QTcF < 450 msec, or QTcF < 480 msec for participants with Bundle Branch Block, in the 12-lead ECG machine-read at Randomization Visit 2. No evidence of a clinically significant abnormality in the central over-read of the 12-lead ECG conducted at Screening Visit 1 that would impact the participant's participation during the study, based on the evaluation of the Investigator. See Section 8.3.3 for further ECG guidance.
- 8. **Asthma Exacerbation:** No asthma exacerbations during run-in period. An exacerbation is defined as worsening of asthma requiring the use of systemic corticosteroids for at least 3 days and/or overnight stay at emergency department

visit, or hospitalization.

- 9. **Maintenance Therapy:** No new systemic corticosteroids for CRSwNP have been started during the run-in period.

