Overall work impairment due to health (%)	100* Q2 / (Q2 + Q4) + [(1 - (Q2 / (Q2+Q4))) x
	(Q5 / 10)]
Activity impairment due to health (%)	10 * Q6

Note (each question with a recall of 7 days):

- Q1 = Currently Employed
- Q2 = Time (hours) missed from work due to health problems during the past seven days
- Q3 = Time (hours) missed from work due to other reasons during the past seven days
- Q4 = Time (hours) actually worked during the past seven days
- Q5 = Productivity affected by health problems while working during the past seven days
- Q6 = Ability to do regular daily activities affected by health problems during the past seven days

Participants not currently employed will only answer Q6. Participants who answer 0 to Q4 will not answer Q5.

If any of the responses used to derive a score are missing or if a participant is not currently employed then the relevant score (work time missed, impairment while working, overall work impairment) will be set to missing.

For those who missed work and did not actually work in the past seven days, the percent overall work impairment due to health will be equal to the percent work time missed due to health.

For SF-36 and WPAI-GH, the intercurrent event of surgery and initiation of a disease-modulating medication for CRSwNP will be handled under the composite strategy by assigning participants their worst observed score prior to the event. All other intercurrent events described under the primary estimand strategy in Section 1.1.2 will be handled using a treatment policy strategy.

For all responder endpoints, participants who undergo nasal surgery or initiate a disease-modulating medication for CRSwNP will be included in the analysis as non-responders for all time points following the event, whichever occurred first. For participants with missing baseline data, a responder status will not be derived. Participants with missing data at a particular post-baseline visit / timepoint will be treated as non-responders for that visit/ timepoint. All other intercurrent events described under the primary estimand strategy in Section 1.1.2 will be handled using a treatment policy strategy.

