#### **6.3.4.2.** Daily Diary

Participants are to complete a daily diary assessment each morning. Table 2 below displays which daily diary records are included for each analysis time period. Any daily diary data collected post the 52-week time period will not be included in the Weeks 49-52 analysis of diary data.

Table 2 Daily Diary Assessment Windows

Analysis for A	M Measures		
Beginning Timepoint (Day)	Ending Timepoint (Day)	Analysis Time Period	
-27	1	Baseline	
2	29	Weeks 1 – 4	
30	57	Weeks 5 – 8	
58	85	Weeks 9 – 12	
86	113	Week 13 – 16	
114	141	Weeks 17 – 20	
142	169	Weeks 21 – 24	
170	197	Weeks 25 – 28	
198	225	Weeks 29 – 32	
226	253	Weeks 33 – 36	
254	281	Weeks 37 – 40	
282	309	Weeks 41 – 44	
310	337	Weeks 45 – 48	
338	365	Weeks 49 – 52	

Note: There is no Day 0 in CDISC reporting. Days -27 to -1 are immediately pre-randomization and Day 1 is the day of randomization (Visit 2). For the baseline time period, all values from Day -27 to Day 1 will be included in the baseline average; however, there must be a minimum of 4 non-missing values from Day -6 to Day 1 inclusive in order to derive the baseline, otherwise it will be set to missing.

Note: For each 4-week post-baseline time period the average will only be derived if there are non-missing values for at least 4 days out of 7 in at least 3 out of 4 weeks, with at least 15 minimum values, otherwise it will be set to missing.

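### The SAP's minimum-data check for the diary baseline is shifted one day from the randomization criterion, so a properly randomized participant can have no VRS baseline and drop out of a co-primary analysis

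*SAP*

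**What the plan says.** **Eligibility.** Protocol 5.3 sets two diary conditions over the same week. Criterion 2 is "Mean nasal obstruction VRS of 2 or greater over the last 7 days preceding Visit 2 (excluding Visit 2"), and criterion 3 is "eDiary compliance for at least 4 out of the last 7 days preceding Visit 2 (excluding Visit 2"). SAP Table 2 notes that there is no Day 0 and that Day 1 is Visit 2, so this week is Day -7 to Day -1.

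**Baseline.** In SAP 4.1.2, "the average will be based on the non-missing data from Day -27 to Day 1 inclusive". A separate data-sufficiency condition applies: "There must be a minimum of 4 non-missing values from Day -6 to Day 1 inclusive in order to derive the baseline". The note to Table 2 (SAP 6.3.4.2) repeats it. If the condition fails, the baseline is set to missing and nothing is derived in its place.

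**Use of the baseline.** The co-primary response is change from baseline, and the MMRM in SAP 4.2.2 also has baseline score as a covariate. For responder endpoints, SAP 4.4.1 says: "For participants with missing baseline data, a responder status will not be derived".

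**Day 1 collection.** The Schedule of Activities lists the VRS and an eDiary compliance check at Visit 2. It states that "eDiary will be completed by participants in the morning between Screening Visit (V1) and V16", and footnote f that "All questionnaires should be performed before any other assessments on each particular visit".

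**The concern.** Both windows are 7 days long and both require 4 entries, but the SAP window drops Day -7 and adds Day 1. A participant can therefore pass the protocol's check, be randomized and dosed, and then be treated as having too little run-in data for a baseline. The entry that made the difference, on Day -7, lies inside the Day -27 to Day 1 averaging window and also counted toward criterion 2.

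Such a participant remains in the FAS but has no change score and no baseline covariate. They are lost from:

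- the nasal obstruction VRS co-primary;
- the rhinorrhoea, loss of smell and Weeks 21-24 nasal obstruction secondaries;
- the other VRS and overall VAS endpoints, and the VRS responder endpoints.

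The planned analyses do not recover them. The sensitivity analyses in SAP 4.2.3 impute post-baseline data and keep the primary model's covariates. A score of 3 assigned after surgery or disease-modulating medication still has no baseline to be subtracted from it. NP score, Lund Mackay and SNOT-22 use the visit-based baseline and are unaffected.

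**Working it through.** **1. The plan's own figures.** Inputs from SAP section 5: 118 evaluable per arm, difference 0.70, SD 0.84, two-sided 5%.

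- Evaluable per arm: 125 × 0.95 = 118.75, taken as 118.
- Standard error: 0.84 × √(2/118) = 0.1094.
- Smallest significant difference: 1.96 × 0.1094 = 0.214 (the plan states -0.21).
- Power: Φ(0.70/0.1094 − 1.96) = 0.999996 (the plan states >99%).

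Both figures are reproduced.

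**2. Which patterns fall in the gap.** There are 8 relevant days (Day -7 to Day -1, and Day 1), so 2⁸ = 256 patterns of present or missing entries.

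- 128 patterns meet criterion 3 (at least 4 entries on Day -7 to Day -1).
- 20 of those 128 fail the SAP check (fewer than 4 entries on Day -6 to Day 1).
- All 20 have the same form: Day -7 present, exactly 3 of Days -6 to -1 present (C(6,3) = 20 ways), Day 1 missing.
- All 128 pass a check over Day -7 to Day 1.

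**3. How often.** The documents give no run-in diary completion rate, so these are assumptions. Let p be the completion probability on each day before Visit 2 and q that on Day 1, with independent days. Then

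P(no baseline | criterion 3 met) = 20 p⁴ (1−p)³ (1−q) / P(Bin(7, p) ≥ 4)

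For p = 0.7 and q = 0.95: 20 × 0.2401 × 0.027 × 0.05 / 0.8740 = 0.0074, and 250 × 0.0074 = 1.85.

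| Daily completion p | q = 0.95 | q = 0.90 | q = p |
|---|---|---|---|
| 0.7 | 0.74% (1.9 of 250) | 1.48% (3.7) | 4.45% (11.1) |
| 0.8 | 0.34% (0.85) | 0.68% (1.7) | 1.36% (3.4) |
| 0.9 | 0.07% (0.16) | 0.13% (0.3) | 0.13% (0.3) |

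Day 1 is a clinic visit at which questionnaires come first, so the q = 0.95 and q = 0.90 columns are the more plausible. The q = p column is an upper range.

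**4. Effect on power.** Take the largest loss shown, 11 participants in total on top of the planned allowance: 118 − 5.5 = 112.5 per arm. Power is 0.99999, and the smallest significant difference moves from 0.214 to 0.220.

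**The case against.** The two rules serve different purposes, and neither document says that meeting one guarantees the other. Criterion 3 is an entry condition. The SAP rule is a data-sufficiency condition for a baseline that runs through the day of randomization. The SAP window also has a logic of its own: Day -27 to Day 1 divides into four 7-day weeks, Day -6 to Day 1 is the last of them, and 4 of 7 matches the post-baseline weekly rule. On this reading, a participant with 3 entries in the final baseline week fails a recency threshold the SAP was free to set. Few people would be affected, the sample size allows for 5% non-evaluable, and power does not move. Finally, criterion 3 does not define eDiary compliance, so equating it with a completed VRS entry is an interpretation.

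Most of this stands as a limit on size. The likely count is nought to two, the upper range should carry little weight, and the interpretation of compliance has to be stated, although a completed entry is its natural meaning. What it does not supply is a reason to discard a participant whose entries satisfied the protocol's own 4-of-7 rule and lie inside the SAP's averaging window. The SAP offers no rationale for doing so. The 5% allowance absorbs the loss numerically, but that is no reason to incur an avoidable one.

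**Conclusion.** The concern holds and is minor. The current text of the two documents allows a participant to meet criterion 3, be dosed and have no diary baseline. That removes them from one co-primary analysis while they remain in the FAS.

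With Day 1 95% complete, the expected number is about 0 to 2 of 250 for daily completion of 70% to 90%. The least favourable case examined gives about 11. These counts assume independent days and that compliance means a completed VRS entry; the completion rates are assumptions, not figures from the plan. Power for the VRS co-primary stays above 99.99%. No between-arm bias is expected, because the exclusion depends only on diary entries made before or on the day of randomization. What remains is an avoidable exclusion caused by a one-day difference between the protocol and the SAP.

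**What to change.** In SAP 4.1.2 and the note to Table 2, count the minimum of 4 non-missing values over Day -7 to Day 1 inclusive. Keep the average over Day -27 to Day 1. Everyone who meets criterion 3 then has a baseline, and every baseline derivable under the present rule keeps its value. Make the change before unblinding.

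The cost is one number in two places. The small drawback is that the check then spans 8 days, so it no longer coincides with the last 7-day baseline week or the 4-of-7 pattern used after baseline.

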#### 4.1.3. Multicenter Studies

For the purposes of covariate adjustment in the statistical analysis, countries will be grouped into the following 3 regions: Europe (EU); United States (US); Rest of World (RoW). The countries that form these regions will include:

- Europe (EU): Belgium; Germany; United Kingdom; France; Netherlands; Spain
- United States (US): United States
- Rest of World (RoW): Canada; Argentina; China; Japan

If there are insufficient subjects in each region for the statistical procedures to converge satisfactorily, the combining of regions will be considered.

# 4.2. Primary Endpoints Analyses

#### 4.2.1. Definition of endpoints

The co-primary endpoints are:

- a) Change from baseline in total endoscopic NP score at Week 52 (centrally read)
- b) Change from baseline in mean nasal obstruction score (verbal response scale [VRS]) from Week 49 through to Week 52

The total endoscopic NP score is assessed in the clinic at visits 2, 5, 7, 9, 11, 13, 15 and 16, or early withdrawal visit (weeks 0, 12, 20, 26, 32, 40, 48 and 52). The score is then graded by independent reviewers at a central lab who are blinded to treatment. The total score is reported as the sum of the right and left nostril scores and ranges from 0 to 8, with higher scores indicating greater disease severity. Non-missing scores must be available for both sides for the combined score to be calculated; otherwise the score will be set to a value of 9 to indicate a missing or unreadable value.

The nasal obstruction VRS score will be collected daily in the morning via the eDiary. Each day the participant will indicate the severity of their symptoms giving a score ranging from 0 to 3, with the 4 options indicating no symptoms, mild symptoms, moderate symptoms, and severe symptoms. The daily data will be collapsed into thirteen 4-week time periods, with the value for each time period based on the average of the non-missing days covered by that time period as described in Section 6.3.4.2. For each 4-week time period the average will only be derived if there are non-missing values for at least 4 days out of 7 in at least 3 out of 4 weeks, with at least 15 minimum values, otherwise it will be set to missing.

As described in Section 1.1.2, under the primary estimand, the intercurrent events of (i) surgery and (ii) initiation of a disease-modulating medication for CRSwNP, will be handled using a composite strategy by incorporating occurrence of the event into the definition of the endpoint. Specifically, participants who experience the intercurrent event will be assigned the worst possible value of the relevant score for all assessments following the intercurrent event (i.e. the worst value that it is possible to select on the given scale). This means that a participant who experiences the intercurrent event will be assigned a total endoscopic NP score of 8 for every scheduled clinic visit after the date of the first intercurrent event (regardless of whether the visit occurred) and a nasal obstruction VRS score of 3 for every day after the date of the first intercurrent event. All other intercurrent events described under the primary estimand strategy in Section 1.1.2 will be handled using a treatment policy strategy.

The study is designed to continue collecting data for participants who have prematurely discontinued from randomized treatment and off-treatment data collected for these participants will be included in the analysis. Missing data will be assumed to be missing at random (MAR). Summary statistics will be produced for each visit/4-week time-period by treatment group for the co-primary endpoints.

# 4.2.2. Main analytical approach

#### **Model Specification**

Statistical analyses will be performed using a Mixed Models Repeated Measures (MMRM)
model with covariates of treatment group, baseline score, log(e) baseline blood eosinophil
count, region, previous surgery for nasal polyps, visit and interaction terms for visit by
baseline score and visit by treatment group.

#### **Model Checking & Diagnostics**

 The Kenward-Roger (KR) method [Kenward, 1997] for approximating the denominator degrees of freedom and correcting for bias in the estimated variance-covariance of the fixed

- effects will be used in the analyses. This will be achieved by specifying the DDFM=KR option in the MODEL statement within PROC MIXED.
- For mixed model repeated measures (MMRM) models, an unstructured covariance structure for the R matrix will be used by specifying 'TYPE=UN' in the REPEATED statement.
  - In the event that the model fails to converge, model simplification methods will be considered (e.g., adjusting covariate structure, streamlining timepoints)
- Appropriate graphs will be reviewed as part of the model checking process to ensure that
  distributional assumptions hold. These will include a normal probability plot of the residuals
  and a plot of the residuals versus the fitted values (checking the normality assumption and
  constant variance assumption of the model, respectively).

#### **Model Results Presentation**

- For each visit / time-period, the adjusted mean change from baseline with corresponding standard error for each treatment group will be presented. The estimated treatment difference will be presented together with 95% confidence interval (CI) for the difference and p-value for the inequality comparison.
- The adjusted mean change from baseline for each treatment, with corresponding 95% CIs will also be presented graphically across the visits / time-periods.
- A cumulative distribution function (CDF) plot will also be provided for the change from baseline by treatment group

# **Additional Analysis**

- The same primary endpoint analysis will be performed using FAS-Modified analysis set
- The same analyses will be performed with the intercurrent event strategy described under the supplementary estimand.

